**Table 1: Outcomes/ Measures**

**Weight (primary outcome)**, by electronic scale measured in pounds as the average of two measures (three measures if difference between the first two is > 1 pound), and height (baseline only, measured to the nearest 1/8 inch). SECA 874dr scales will be used.

| Secondary Outcomes  |  |
|--|--|
| Biomarkers  |  |
| --Blood pressure by noninvasive automated monitor (Omron HEM-907XL, Vernon Hills, IL) with a first measure after seated for 5 minutes and two repeat measures at 1-minute intervals. The average of the 3 measurements will be used.   |  |
| --For blood work fasting status is requested for 9 hours and fasting status at phlebotomy is assessed. Blood tests performed at LabCorp includes: total cholesterol, HDL cholesterol, LDL cholesterol, triglycerides, A1c, ALT, and CRP. Inflammatory markers, to be assess on frozen specimens after all are collected will include: interleukin (IL)-6, tumor necrosis factor (TNF)-alpha, insulin, and leptin. |  |
| --Skin carotenoids, Reflection Spectroscopy Device ("Veggie Meter")    |  |
| Questionnaires:   |  |
| --Demographics, literacy screener  and medical history (baseline only)   |  |
| --Diet assessment: brief assessment of diet quality ,  adapted PREDIMED checklist   |  |
| --Detailed assessment of diet quality: Willett Food Frequency Questionnaire, 2007 booklet administered as REDCap survey    |  |
| --Physical activity and sedentary behaviors: GPAQ for physical activity and sedentary behavior ,  participant report of monitored steps   |  |
| --Quality of life (EQ5D  )  |  |
| --Food insecurity   |  |
| --Predictors of behavioral change  |  |
| -- weight loss self-efficacy ,  self-regulation ,  eating behaviors ,  and self-weighing behaviors   |  |
| --Medications for high BP, high blood lipids, diabetes, and weight loss (self-report with EHR review)  |  |
| --Adverse outcomes, CVD events, ER visits, and hospitalizations (follow-up only)   |  |
| --Acceptability (follow-up only)   |  |
| Diet and PA goals and success achieving goals (collected by web-based intervention platform)   |  |
| Other   |  |
| --EHR to assess/confirm adverse health outcomes  |  |

## 6 Analysis Populations

Potential participants who were screened but not randomized will not be included in any efficacy or safety analyses of study data.

### 6.1 Intent-to-Treat Population (ITT)

The Intent-to-Treat population will consist of all subjects who are randomized. No protocol violations will lead to exclusion from the intent-to-treat population. Subjects in the intent-to-treat population will be grouped according to the treatment assigned by the randomization procedure. This population will form the basis for the primary and

secondary efficacy analyses of study data as well as for safety analyses. In this analysis, the mixed model with account for missing as missing at random.

Analysis for the primary outcome will be conducted with a dummy variable for randomization group. After the biostatistical team and MPIs are confident with analysis, the actual randomization status will be revealed.

## **6.2 Intent-to-Treat Population (ITT) using Missing Weights from the Medical Record**

For missing weights, we will review the electronic health record and use weights as follows:

Weights will be used if they fall within the time frame allowed for follow-up measurement visits (see above Sect 5.4) and if consistent with prior weights (to avoid the occasional situation where pounds are mistakenly entered as kilograms). If more than one weight is available within the specified time window, the weight closest to the median for the window will be used. After the additional of weights so identified from the electronic medical record, we anticipate less than 5 % of follow-up weights will be missing.

## **6.3 Intent-to-Treat Population (ITT) censoring data for those with greater than 5% weight loss attributed to medical condition**

For participants with > 5% weight loss at any follow-up time point, an electronic health record chart review will be conducted. If weight loss is attributed to a new medical condition typically associated with weight loss (for example, pancreatic cancer), participant outcome data will be censored from the time of diagnosis onward.

## **6.4 Intent-to-Treat Population (ITT) censoring data for those using weight loss medication**

Note: at baseline, potential participants with diabetes on GLP-1 agonists and/or other medications used for diabetes that may be associated with weight loss were allowed to participate. For those without diabetes, current use of weight loss medication was an exclusion criterion. For participants who initiated use of GLP-1 agonists during the course of the study, weight change data will be censored at the time point where use of these medications is documented. We will not censure data for use of other medications that may impact weight loss when impact on weight change is typically minimal to modest (< 3%).

Added 10/28/24. Medications listed as weight loss

Amendment added 4/19/25: as only 2 pts had medical illness and 1 had bariatric surgery, we will combine 6.3 and 6.4

## **6.5 Per Protocol Population**

The Per Protocol Population for assessment of weight change at 24 months will be a subset of the ITT population and will exclude participants who did not adequately adhere to the protocol as defined below for their assigned treatment arm, for whatever reason, and did not attend the final measurement visit.

Specifications to be included in per protocol analysis.

Both study groups.

- Measurement visits: attends the final measurement visit

Group 1: Med-South (Phase 1 = 4 months; Phase 2 = 8 months; Phase 3 = 12 months. There were 30 planned visits over 24 months; 75% would be 22 visits total; 75% of each = approximately 3, 10, 9, respectively.)

- **Phase 1** -- 4 major counseling sessions: attended at least 3 visits
- **Phase 2** -- 14 sessions planned (8 weekly → 6 monthly; optional brief follow-up): attended at least 10 visits.
- **Phase 3** -- 12 sessions planned (monthly; optional brief follow-up): attended at least 9 visits.

Group 2 WW

- As of 9/10/24, we have not received data from WW, though we are expected to receive these data. When available we will operationalize definition akin to 75% engagement of group 1.

We will also assess per protocol outcomes at 4 and 12 months for those meeting definitions as above and will follow-up data at these time points respectively.

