Behavioral content enhancements: We will enhance the initial 4 month lifestyle phase with additional content that focuses on preparing participants for the weight loss intervention in Phase II by introducing a set of stability skills shown to improve long-term weight management.¹¹² Proposed stability skills enhancements include: 1) learning how to eat healthfully without feeling deprived or dissatisfied; 2) becoming comfortable with frequent self-weighing (making peace with the scale); and 3) navigating inevitable disruptions.¹¹² However, there is still no expectation for weight loss during this phase.

Dietary composition enhancements/rationale: The tested Med-South program recommended frequent consumption of vegetable oils (including olive oil, but not specifically recommending olive oil) and nuts, including peanuts.¹¹³ Given the benefits of extra virgin olive oil as demonstrated in PREDIMED,²¹ we will encourage consumption of extra virgin olive oil for those who like the taste and can afford it. However, the intervention will continue to recommend consumption of low cost and familiar oils such as soybean,

peanut, and canola oil, as the scientific data supporting the positive health effects of vegetable oils with high polyunsaturated fatty acids (PUFAs) content are compelling,¹¹⁴⁻¹¹⁶ including a beneficial effect of omega 6 PUFAs on CVD and total mortality.³⁸ Our rationale for recommending fish ≥ 1 serving per week vs. ≥3 servings is 1) cost-related, as fish can be expensive, and 2) scientific, as most of the benefit from fish consumption is realized with 1 serving per week.¹¹⁷ PREDIMED limited spread fats to < 1 serving per week, but now that non trans-fat tub margarines are available with high-quality fat content (e.g., Smart Balance™ and others), we recommend consumption of high-quality spreads. As sofrito sauce is not commonly consumed in the US, we are not recommending it, but instead, familiar foods made with tomatoes, onions, and garlic such as salsa.

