Phase 3 of DELISH counseling (Maintenance) prioritized three in-person visits (start of year 2, the 18-month halfway point, and the final visit at the 24-month end point) to educate the participants on weight-loss maintenance and how to continue with their goals once the intervention ended. In between these in-person counseling and measurement sessions, counselors provided monthly counseling sessions via phone as needed for each participant. Additional in-between phone call check-ins were available if requested by the participant. These sessions, both monthly and in-between calls, were more flexible and allowed the participants to choose which materials and educational handouts they wanted to focus on before finishing the intervention. This individualized counseling approach allowed for specialization of each participant's interests and needs as they finished up the intervention.

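### SAP 6.5 writes no 4- or 12-month per-protocol rule; read literally, it selects those sets on sessions and a visit that come after the outcome

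*SAP*

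**What the plan says.** SAP 6.5 contains a single definition, and its opening ties it to one endpoint: "The Per Protocol Population for assessment of weight change at 24 months will be a subset of the ITT population". For both arms it lists one measurement condition: "Measurement visits: attends the final measurement visit". For Med-South it adds session bars, derived as follows: "There were 30 planned visits over 24 months; 75% would be 22 visits total". The bar for Phase 1 (months 0-4) is "4 major counseling sessions: attended at least 3 visits". Phase 2 (months 4-12) asks for at least 10 of 14. The bar for Phase 3 (months 12-24) is "12 sessions planned (monthly; optional brief follow-up): attended at least 9 visits". For WW no bar existed at the draft date of 9/10/24; one comparable to 75% engagement was to be set once WW data arrived.

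The section closes: "We will also assess per protocol outcomes at 4 and 12 months for those meeting definitions as above". That sentence goes on to mention follow-up data at those times, with a word apparently garbled, and ends with *respectively*.

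No other section supplies a 4- or 12-month rule. Protocol 9.3 lists only the ITT population, and Protocol 9.4.2 names a Per Protocol Population without defining it. SAP 9.4.1 fits one longitudinal model to all three follow-up visits and repeats it secondarily in the Per Protocol Population, in the singular.

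**The concern.** Per-protocol status at a visit should depend only on what happened up to that visit. Take a Med-South participant who attends all 4 Phase 1 sessions, gives a 4-month weight, and stops counselling in month 10. Adherence to month 4 is complete, yet the literal rule removes this person from the 4-month per-protocol result.

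This matters because later attendance in this trial may respond to earlier weight change. SAP 6.6 accepts that some dropout may be linked to weight. Protocol 6.1.1 (subsection 3.3c) lets the frequency of Phase III contacts vary with a participant's progress. Protocol 6.1.2 reports that in Phase III "counselors provided monthly counseling sessions via phone as needed for each participant". Selecting on later sessions can therefore select, indirectly, on the outcome being analysed.

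At stake are the secondary 4- and 12-month per-protocol estimates: who is in them, how many are lost, and whether a difference reflects adherence or selection. Two programmers could also build different sets from the same text.

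**Working it through.** **1. The plan's own thresholds (SAP 6.5).** 0.75 × 30 = 22.5, and 0.75 × (4, 14, 12) = 3, 10.5, 9. Rounded down, these give 22 and 3/10/9, and 3 + 10 + 9 = 22. The stated figures reproduce.

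**2. How much of the rule follows each outcome (literal reading).** The phases last 4, 8 and 12 months, so they end at the nominal measurement times.
- 4 months: 10 + 9 = 19 of 22 required sessions (86%) come later, plus the final visit.
- 12 months: 9 of 22 (41%) come later, plus the final visit.

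**3. Effect on set size.** The documents give no attendance rate. Assume each session is attended independently with probability 0.8.
- P(≥3 of 4) = 0.819; P(≥10 of 14) = 0.870; P(≥9 of 12) = 0.795.
- Phase 1 bar: 0.819. Phases 1 and 2: 0.819 × 0.870 = 0.713. All three: 0.713 × 0.795 = 0.566.
- Dropped for later sessions: 1 − 0.566/0.819 = 31% of those adherent at 4 months, and 1 − 0.566/0.713 = 21% of those adherent at 12 months, before the final-visit condition.

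Independence is a simplification. It cannot be strictly true if attendance depends on prior weight change, so these figures are only indicative.

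**4. Shift in the mean within Med-South.** If r is the correlation between early loss and later adherence, p the share retained and φ the standard normal density, then shift = r × SD × φ(z₁₋ₚ)/p. Positive means more loss. The documents give no r, no p and no 4- or 12-month SD; SAP 9.6 gives only 7.3% at 24 months.
- r = 0: shift 0.
- r = 0.1 to 0.3, p = 80% to 40%, SD 5: 0.17 to 1.45 points. With SD 7.3: 0.26 to 2.12 points.
- Using the retention implied by step 3 (0.870 × 0.795 = 69%), SD 4 and r = 0.2: 0.2 × 4 × 0.353/0.69 = 0.41 points.
- If r is negative, the sizes are the same and the sign reverses.

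**5. Between-arm effect.** This is the Med-South shift minus the WW shift. Assume SD 7.3, the same r = 0.2 in both arms, and 50% retained in Med-South (shift 1.16).
- WW keeps 80% (shift 0.51): +0.65 points.
- WW keeps 50%: 0.
- WW keeps 30% (shift 1.69): −0.53 points.

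The sign turns on the WW bar, which the SAP had not set.

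**6. Literal rule against phase-matched rule.** This is a simulation of Med-South with no treatment effect. Assumed: SD 4 at 4 months and 6 at 12 months, correlation 0.7 between them, and log-odds of attending raised by 0.2 to 0.6 per SD of prior loss.

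| Outcome | 24-month rule | Phase-matched rule |
|---|---|---|
| 4 months | +0.5 to +1.35 | about 0 |
| 12 months | +0.9 to +2.4 | +0.35 to +1.0 |

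With no link between attendance and prior loss, every entry is about 0.

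**The case against.** **The literal reading is not the only one.** The definition is introduced for the 24-month endpoint, the bars are listed by phase, the phases end at the measurement times, and the last sentence ends with *respectively*. Phase 1 alone at 4 months, and Phases 1 and 2 at 12 months, is a plausible intent. This stands: the documents do not settle that the 24-month rule governs the earlier sets. But the phase-matched reading is nowhere written, the only measurement condition listed is the final visit, and SAP 9.4.1 speaks of one Per Protocol Population for a model covering all visits.

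**A reader might infer that the rule favours early losers in Med-South.** The documents do not support that direction. SAP 6.6 says dropout may be related to weight but gives no sign. Protocol 6.1.1 steps contacts up for non-responders and by progress, and Phase III calls were given as needed. People doing well could need fewer calls and miss the 9-session bar, which would select against losers.

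**A reader might also take a within-arm shift as bias in the comparison.** It is not. The final-visit condition applies to both arms and WW is to have its own engagement bar, so the net effect can be positive, zero or negative (step 5).

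**A reader might infer that any 4-month difference must be an artefact,** since the protocol says of Phase I that "there is still no expectation for weight loss during this phase". That describes what is asked of participants and does not predict zero effect. The background in Protocol 6.1.1 suggests that dietary change alone may have produced weight loss in the earlier study's lifestyle-only group.

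**The analysis is secondary.** This also stands, and it limits the weight of the point.

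**Conclusion.** The point holds as a gap in the definition with a real but unsigned risk of bias. If the closing sentence is followed as written, the 4- and 12-month per-protocol sets depend on events after the outcome: 86% and 41% of the required Med-South sessions respectively, and the final visit in both arms. That is firm arithmetic from the SAP, conditional on the literal reading.

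The size of any bias is not firm. Within Med-South, plausible but assumed inputs give anything from zero to roughly one or two percentage points, in either direction. The between-arm effect cannot be stated until the WW rule exists. The 31% and 21% losses rest on independent attendance at 0.8.

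The primary 24-month ITT contrast, the sample size and the power figures are unaffected. The change is still worth making, because it removes the ambiguity at almost no cost and, if phase-matching was always intended, merely writes it down.

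**What to change.** Replace the closing sentence of SAP 6.5 with cumulative, visit-specific sets:
- **4 months:** at least 3 Phase 1 sessions and the 4-month measurement visit.
- **12 months:** at least 3 Phase 1 and at least 10 Phase 2 sessions, and the 12-month measurement visit.
- **24 months:** the present list of inclusion requirements, once reconciled with the section's opening sentence. That sentence excludes people who both failed to adhere and missed the final visit, whereas the list requires adherence and attendance for inclusion.

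Set the WW engagement bar over the matching periods (months 0-4, 0-12 and 0-24). State in SAP 9.4.1 that 4- and 12-month contrasts from a model fitted in the 24-month set are not reported as per-protocol results.

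SAP 9.4.1 carries a note from a review of the analysis in May 2025, so outcomes may already be known. If so, state which rule was used, show the phase-matched version beside it, and label any change as made after the results were seen.

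The cost is wording and two extra flag variables, with no new data. There are two downsides. The three sets will contain different people and need separate tabulation. Some selection on attendance before month 12 also remains in the 12-month set (+0.35 to +1.0 points in step 6, under its assumptions).

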## **6.6 Sensitivity Analysis and missing data**

As outlined above, we will obtain weights from the electronic health record for study participants who did not return for measurement visits. These weights are collected on high quality electronic scales. The weight protocol in the clinic does not include removing shoes, though we expect some variability of shoe removal. We will not adjust weights obtained from the medical record for shoe removal.

After adding weights within range from the electronic health record, we anticipate that > 90% of study participants will have weights within the specified measurement windows. After including these weights, we anticipate missing weights will be less than 5%. If less than 5% of weights are missing at 24 months, the data will be analyzed by linear mixed models. If 5% or more of the weights at 24 months are missing, we will proceed as follows.

We made every effort to prevent missing data and to minimize attrition, however some dropouts occurred. We know the reasons for some dropouts but not all cases. We also know that some dropouts may be related to the underlying weight outcome so the missingness is not random. To address the missing data, we will first compare respondents and non-respondents for differences on values of selected baseline variables to assess for missing at random. We will also conduct a series of sensitivity analyses to evaluate the robustness of conclusions drawn from the primary model to departures from missing at random (MAR) assumption by comparing the magnitude of the primary treatment contrast. The linear mixed model with maximum likelihood estimation is capable of dealing with data that are MAR. In case data are not missing at random, we will use 1) multiple imputation to include auxiliary information about the missingness; 2) shared-parameter models where one variable is the efficacy outcome and the second variable is time to dropout, linked by a set of latent variables that are assumed to influence both the outcome and the time to dropout; (3) patterning-mixture model, with models for each pattern of missingness (e.g., by study phase); and (4) worst-case imputation, with baseline carried forward for intervention participants and best observation carried forward for control participants.

# **7 Outcome Definitions**

## **7.1 Primary Study Endpoint**

The primary outcome for this study is the percent change in body weight defined as (Follow-up weight – baseline weight)/baseline weight x 100%.

We will also assess proportions of participants losing ≥ 5% baseline body weight at each follow-up visit.

## **7.2 Key Secondary Outcomes**

Key secondary outcomes include changes in the following outcomes from baseline to 24 months.

- blood pressure
- A1c

- markers of inflammation
- skin carotenoids
- self-reported dietary patterns

### **7.3 Additional Secondary Outcomes**

We will also assess process variables including attendance, fidelity, and acceptability of the Med-style dietary intervention), and key behavioral and psychosocial variables, including self-regulation/monitoring skills, self-efficacy, motivation, and quality of life. If there is a material treatment effect (> 2.5% difference in weights per primary outcome), we will also undertake an Economic analysis as outline in Objective D.

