9 STATISTICAL CONSIDERATIONS

9.1 STATISTICAL HYPOTHESES

This randomized trial will compare the effects of a Mediterranean-style (Med-style) dietary pattern intervention to an augmented usual care control group in primary care clinics. The objectives of this trial are:

Primary Aim (efficacy): Weight loss at 24 months. Hypothesis: Mean weight loss in the intervention group will exceed that in augmented usual care by $\geq 4\%$ of initial body weight (e.g., $\geq 5\%$ intervention, $\sim 1\%$ control).

Secondary weight outcomes: Assess difference between study groups in proportion losing $\geq 5\%$ body weight and differences in mean weight loss and proportion losing $\geq 5\%$ across 3 pre-specified subgroups: 1) with vs. without diabetes; 2) females vs. males; and 3) Whites vs. African Americans.

Secondary Aim 1—Physiologic and Lifestyle Outcomes: Assess change in blood pressure, A1c, markers of inflammation, skin carotenoids, and self-reported dietary patterns by study group.

Secondary Aim 2—Process and Psychosocial Factors: Assess process variables (attendance, fidelity, and acceptability of the Med-style dietary intervention), and key behavioral and psychosocial variables, including self-regulation/monitoring skills, self-efficacy, motivation, and quality of life.

Secondary Aim 3--Economic Outcomes: Assess implementation cost, and incremental cost-effectiveness of the intervention relative to control in terms of cost per percentage reduction in weight (i.e., kg lost) and cost per quality adjusted life years (QALYs) gained.

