9.4.3 ANALYSIS OF THE SECONDARY ENDPOINT(S)

Analysis of Secondary Objectives (1-2)

The ITT Population will be used in the primary analysis of all secondary outcomes. Similar ANCOVA methods to those described above will be used to compare groups on each of the secondary outcomes; for any outcome measured at baseline, the corresponding ANCOVA will control for baseline value in addition to the covariates noted above. Blood pressure will be averaged over three repeated measurements at each visit. Because they are of secondary interest, tests on secondary outcomes will each be conducted at the 5% significance level with no adjustments for multiple comparisons. All estimates of effect size will be accompanied by 95% confidence intervals. Data from all secondary outcomes will be presented regardless of extent of “significance”. Descriptive summaries of process data (attendance at intervention contacts, fidelity to intervention delivery, and acceptability of the Med-style dietary pattern) will be provided for participants randomized to Group 1 in the ITT Population. No inferential statistics (p-values or confidence intervals) will be presented.

Analysis of Secondary Objective 3 (Economic Analysis)

We plan to conduct both a budgetary impact assessment and a cost-effectiveness analysis. The budgetary impact assessment will quantify the total and per participant costs of intervention delivery from the health system perspective using an Activity Based Costing (ABC) approach and cost tracking forms that the health economist ([name])¹⁵⁸⁻¹⁶⁰ has developed and refined in past behavioral trials. Using this approach, all relevant labor, materials and supplies, contracted services, and other relevant costs required to deliver the interventions will be captured by key activities. This information will allow policy makers to identify the total and per capita fixed and variable costs of the intervention and to forecast required budgets, should the intervention expand beyond the trial phase. The non-sunk cost estimates will also feed into the cost-effectiveness analysis.

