## Date of current draft.

The draft was prepared on 9/10/24, after all participants were randomized but before analysis of outcomes.

3

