## Objectives

a) The primary objective of the DELISH Study is to determine if mean weight loss in the intervention group will exceed that in augmented usual care by  $\geq 4\%$  of initial body weight (e.g.,  $\geq 5\%$  intervention,  $\sim 1\%$  control).

Secondary objectives include:

b) assessing difference between study groups in proportion losing  $\geq 5\%$  body weight and differences in mean weight loss and proportion losing  $\geq 5\%$  across 3 pre-specified subgroups: 1) with vs. without diabetes; 2) females vs. males; and 3) Whites vs. African Americans,

c) assessing change in blood pressure, A1c, markers of inflammation, skin carotenoids, and self-reported dietary patterns by study group,

d) assessing process variables (attendance, fidelity, and acceptability of the Med-style dietary intervention), and key behavioral and psychosocial variables, including self-regulation/monitoring skills, self-efficacy, motivation, and quality of life, and

e) assessing implementation cost, and incremental cost-effectiveness of the intervention relative to control in terms of cost per percentage reduction in weight (i.e., kg lost) and cost per quality adjusted life years (QALYs) gained.

5

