### 9.4.4

### Secondary Analyses

The ITT Population will be used in the primary analyses of all secondary outcomes. Similar ANCOVA methods to those described in the primary outcome analyses will be used to compare groups on each of the secondary outcomes. For any outcome measured at baseline, the corresponding ANCOVA will control for baseline value in addition to the covariates noted above. Because they are of secondary interest, tests on secondary outcomes will each be conducted at the two-sided 5% significance level without adjustments for multiple comparisons. All estimates of effect size will be accompanied by 95% confidence intervals. Data from all secondary outcomes will be presented regardless of extent of "significance".

Descriptive summaries of process data (attendance at intervention contacts, fidelity to intervention delivery, and acceptability of the Med-South dietary pattern) will be provided for participants randomized to the Med-South dietary pattern intervention group in the ITT Population. No inferential statistics (p-values or confidence intervals) will be presented.

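### SAP 7.3 commits to the economic analysis only if the weight difference exceeds 2.5%, although SAP objective (e) and the protocol plan it without condition

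*SAP*

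**What the plan says.** SAP 7.3 (Additional Secondary Outcomes) states: "If there is a material treatment effect (> 2.5% difference in weights per primary outcome), we will also undertake an Economic analysis". It refers the reader to Objective D ("undertake an Economic analysis as outline in Objective D"). In the SAP's list of objectives, (d) covers process and psychosocial variables. The economic objective is (e), which carries no condition: "assessing implementation cost, and incremental cost-effectiveness of the intervention relative to control in terms of cost per percentage reduction in weight", together with cost per QALY.

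The protocol is also unconditional. Secondary Aim 3 in Protocol 9.1 reads "Assess implementation cost, and incremental cost-effectiveness of the intervention relative to control". Protocol 9.4.3 says "We plan to conduct both a budgetary impact assessment and a cost-effectiveness analysis", and of the first part, "The budgetary impact assessment will quantify the total and per participant costs of intervention delivery from the health system perspective". The same section plans incremental cost per kilogram lost, incremental cost per QALY with EQ-5D differences as the denominator, one-way and probabilistic sensitivity analyses, and acceptability curves.

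The SAP dates its draft 9/10/24, "after all participants were randomized but before analysis of outcomes". The sentence in 7.3 carries no later date.

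**The concern.** A named secondary aim has become conditional in one sentence of the SAP. The sentence gives no reason for the condition or for the value 2.5, and the SAP's own statement of objectives was not changed to match. An analyst following 7.3 and one following objective (e) would do different things with the same result.

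The condition also sits poorly with what it controls. Delivery costs, and hence the budgetary impact assessment, can be estimated whatever happens to weight. Cost per QALY takes its denominator from EQ-5D, not weight. Of the planned economic outputs, only cost per kilogram depends directly on the weight difference.

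At stake is a trial that reports a statistically significant weight benefit with no cost figures beside it, which would leave a decision maker unable to judge affordability or value.

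**Working it through.** **Inputs.** SD of percent weight change 7.3, two-sided alpha 0.05, 1:1 allocation, 20% attrition, and differences of 3 and 4 points (Protocol 9.2; SAP 9.6). Total randomized 360. As an alternative to 20% attrition I use 5% missing, the upper end of what SAP 6.2 and 6.6 expect once health-record weights are added. I use a normal approximation with no gain from covariates, and read the condition as applying to the point estimate of the 24-month difference in favour of the intervention.

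**Reproducing the plan's power.** For 350 randomized, n per arm = 350 x 0.8 / 2 = 140.
- SE = 7.3 x sqrt(2/140) = 0.873.
- Power at 4 points = Phi(4/0.873 - 1.96) = 0.996 (stated 99.5%).
- Power at 3 points = Phi(3/0.873 - 1.96) = 0.930 (stated 93%).

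The inputs are therefore those the sponsor used.

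**Smallest significant estimate at 360.**
- 20% attrition: n = 144 per arm; SE = 7.3 x sqrt(2/144) = 0.860; 1.96 x SE = 1.69.
- 5% missing: n = 171 per arm; SE = 7.3 x sqrt(2/171) = 0.789; 1.96 x SE = 1.55.

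Both lie below 2.5, so there is a band of estimates, 1.69 (or 1.55) to 2.5, that are significant but do not trigger the economic analysis.

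**Probability of landing in the band.** P = Phi((2.5 - d)/SE) - Phi((c - d)/SE), where d is the true difference and c the smallest significant estimate. The first term alone is the probability that the analysis is not triggered for any reason.

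| True difference | Missing | Not triggered, any reason | Significant and not triggered |
|---|---|---|---|
| 4 | 20% | 0.041 | 0.041 - 0.004 = 0.037 |
| 4 | 5% | 0.029 | 0.029 - 0.001 = 0.028 |
| 3 | 20% | 0.281 | 0.281 - 0.063 = 0.217 (unrounded terms) |
| 3 | 5% | 0.263 | 0.263 - 0.033 = 0.230 |

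**An estimate exactly at 2.5.**
- 20% attrition: z = 2.5/0.860 = 2.91, p = 0.004; 95% CI 2.5 +/- 1.69 = 0.81 to 4.19.
- 5% missing: z = 2.5/0.789 = 3.17, p = 0.002; 95% CI 2.5 +/- 1.55 = 0.95 to 4.05.

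An estimate that just fails the condition would thus be clearly different from zero and still compatible with the planned 4 points.

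**Sensitivity to the SD.** At 144 per arm the band disappears only if the SD reaches about 10.8 (1.96 x 10.8 x sqrt(2/144) = 2.49), well above the planning value.

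**The case against.** The best defence is that the SAP is the later and more detailed document. Protocol 9.4.1 describes the protocol text as the plan submitted with the protocol and says a fuller SAP was prepared before outcomes were assessed; a note closing Protocol 9.4.3 also points to a separate SAP. On that reading 7.3 is a deliberate, pre-specified narrowing. This largely explains the difference from the protocol. It does not explain the conflict inside the SAP between 7.3 and objective (e), and nothing records or justifies the narrowing.

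The sentence also does not forbid the analysis below 2.5; it only fails to commit to it. That is correct, and it is why the point is worded as a missing commitment. Under the planned 4 points the chance of harm is small, which also stands. The wrong letter is probably a slip, since the sentence names the economic analysis.

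A reader might infer two stronger points. The first is a breach of SAP 9.4.4: "Data from all secondary outcomes will be presented regardless of extent of" significance. That sentence follows text on ANCOVA comparisons and 5% tests of secondary outcomes, and in Protocol 9.4.3 its counterpart sits under objectives 1-2, apart from the economic heading. It does not govern whether the economic analysis is started. The second is that selecting on 2.5% makes the reported cost per kilogram misleading. A ratio with an estimated effect in its denominator is biased without any threshold as well, so the documents do not show that the condition makes it worse overall.

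**Conclusion.** The point holds as an inconsistency that should be fixed. SAP 7.3 leaves Secondary Aim 3 without a firm commitment whenever the estimated difference is 2.5 points or less, against the SAP's own objective (e) and more narrowly than the protocol. A significant weight result with no economic analysis triggered has a probability of 3-4% if the true difference is 4 points and 22-23% if it is 3. Counting non-significant results too, the figures are 3-4% and 26-28%.

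These rest on the planning SD, 360 randomized, 20% attrition or 5% missing, an unadjusted standard error, and the reading of the condition as a 24-month point estimate. Covariate adjustment would probably lower the standard error and widen the significant band below 2.5.

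A reader might suspect that the threshold was chosen after seeing results. The documents do not support that: the SAP draft is dated before outcome analysis and this sentence has no later date. The primary test and its error rate are unaffected.

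**What to change.** In SAP 7.3, delete the 2.5% condition and change the reference from Objective D to objective (e). Suggested text: *We will also undertake the economic analysis in objective (e), as described in Protocol 9.4.3, whatever the weight result.* Both the budgetary impact assessment and the incremental cost-effectiveness analysis would then be carried out, with uncertainty shown by the probabilistic sensitivity analysis and acceptability curves already planned.

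The cost is that the economic work is done even when the weight effect is small. Cost per kilogram is then unstable and has to be read with its uncertainty. The change adds no data collection to the plan: EQ-5D and medication use are scheduled at every measurement visit, and the costing questionnaires and claims data are already in Protocol 8.1.2.
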